2.0 Background

2.1 Scientific Background and Gaps

Osteoarthritis (OA) affects 54.4 million US adults and 23.7 million (43.5%) have arthritis-attributable activity limitation¹. As the condition progresses, pain and functional disability increase. Patients usually begin treatment with conservative measures including physical therapy and administration of nonsteroidal anti-inflammatory drugs before obtaining a corticosteroid injection². Corticosteroid injections have a patient-specific duration that often provide relief for a month before the effects begin to taper with most individuals returning to baseline by 2-3 months post injection^{3,4}.

Unfortunately, data on intraarticular injections is not robust and primarily focused on hip, knee, and disease processes rather than the glenohumeral joint⁶⁻⁸. For example, steroid concentrations have been studied in adhesive capsulitis, where 20 and 40mg of triamcinolone acetonide were used with no statistical significance between the two⁶. When a placebo was added, both doses were better than the placebo, but once again no difference was seen between the two steroid concentrations⁷. Another study, looking at knee osteoarthritis, found that high dose steroids had a larger effect on duration⁸, but other studies have shown no difference in duration between the 40mg and 80mg concentration of triamcinolone acetonide⁹.

Intraarticular injections do have adverse effects. Similar to steroids taken orally or intravenously, intraarticular injections have a similar side effect profile. Fortunately, intraarticular injections are localized, by the nature of the procedure, and the chances of experiencing a significant side effect is rare^{10,11}. The most common side effects are steroid flare, allergic reaction, facial erythema, hypo- pigmentation, fat pad necrosis, cutaneous atrophy, and a transient increase in blood glucose¹¹. Some of the rare side effects have been seen in case reports include idiopathic central serous chorioretinopathy, decrease in breast milk production, sepsis, tendon rupture, and cataracts¹¹. In addition, the administration of steroid injections are limited to being done every three months due to risk of weakening tendons, and acceleration of cartilage loss^{11,12}.

There is a void of literature for understating the ideal injectable steroid concentrations in glenohumeral osteoarthritis. Because of this, providers who perform intraarticular injections tend to perform them based on prior training experience or anecdotal evidence¹³. We aim to evaluate the ideal steroid concentration that will maximize treatment effect for glenohumeral osteoarthritis, but at the same time minimize side effects, and better train our future providers.

2.2 Previous Data

Not Applicable

2.3 Study Rationale

There have been no studies to date examining the optimal steroid concentration for injections of the glenohumeral joint for osteoarthritis. This is important because corticosteroid injections are not without risk. Better patient care hinges on the correct balance between an effective dose of steroid and minimizing potential adverse effects. Current practice is based completely on expert opinion and standard of care rather than scientific evidence.

3.0 Inclusion and Exclusion Criteria

3.1 Inclusion Criteria

- An X-ray with Radiographic evidence of OA
- 18 years of age or older
- Clinical diagnosis established due to symptoms that will include pain attributed to glenohumeral osteoarthritis, pain with range of motion, and/or functional limitations longer than 3 months.

3.2 Exclusion Criteria

- Previous guided steroid injection of the glenohumeral joint within 3 months
- Previous diagnosis of inflammatory arthritis, rotator cuff tear, or immunocompromised
- Previous shoulder surgery
- Allergy to steroid or lidocaine
- A Kellgren and Lawrence classification of 1 or less on radiograph
- Non-English Speaking
- Inability to provide informed consent

3.3 Early Withdrawal of Subjects

3.3.1 Criteria for removal from study

Patients will be withdrawn from the study for safety reasons including failure of subject to adhere to protocol requirements, or withdrawal of subject consent.

3.3.2 Follow-up for withdrawn subjects

If a patient is withdrawn from the study, data collection will be terminated from that time point forward. All prior data collected will be included in the analysis. These subjects will not be

replaced, but instead more subjects may need to be enrolled. The new data will be recorded and analyzed as would any other new enrollee.

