7.2.3 Post-Clinic appointment

Patients will be contacted via telephone at 2 weeks to determine if any significant adverse outcomes have occurred. Patients will be contacted at 2 months, 4 months, and 6 months following the injection by email and/or phone call for completion of the SPADI and assessment of any adverse events that may have occurred as a result of the injection. Patients will also be asked what, if any, pain medications have been used in the month prior to the phone call. Patients will be given the option to complete the SPADI using the REDCap system or on paper. Patients wishing to complete the survey online will be emailed a link to access REDCap. A paper version of the survey will be mailed to the patient if that is their preferred method. A self-addressed stamped envelope will be included with the mailings. If the patient perceives that they have experienced an adverse effect the research coordinator will make a detailed record of the patient experience and the PI of the study will be contacted. .

At 12 months following the initial injection, in addition to a chart review, the patient will be contacted to determine the outcome of their shoulder pain and determine if the patient underwent any additional procedures and/or surgeries to the shoulder.

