10.3 Method of collection of safety information

Safety information will be collected by phone interview during the follow up phone calls as well as review of the electronic medical record.

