10.5 Individuals reviewing the data

All data will be reviewed by members of the research team at completion of the study. Reporting of any adverse events will be reviewed as they occur.

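### Section 3.3.2 ends data collection after every withdrawal, even when consent stands, so planned primary and secondary endpoint data are lost, possibly selectively

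*Combined protocol and SAP*

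**What the plan says.** Section 3.3.1 gives the grounds for removal: "Patients will be withdrawn from the study for safety reasons including failure of subject to adhere to protocol requirements, or withdrawal of subject consent". Only the last ground is a decision by the patient to end participation.

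Section 3.3.2 applies one rule to all of them: "If a patient is withdrawn from the study, data collection will be terminated from that time point forward". Earlier data are kept: "All prior data collected will be included in the analysis". Withdrawn subjects will not be "replaced, but instead more subjects may need to be enrolled".

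The follow-up that this cuts short is set out elsewhere:

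- **Section 7.2.3, 2 weeks:** "Patients will be contacted via telephone at 2 weeks to determine if any significant adverse outcomes have occurred".
- **Section 7.2.3, 2, 4 and 6 months:** SPADI, adverse events and pain medication, collected remotely.
- **Section 7.2.3, 12 months:** "At 12 months following the initial injection, in addition to a chart review, the patient will be contacted" about the shoulder outcome and any further procedures.
- **Section 10.3:** "Safety information will be collected by phone interview during the follow up phone calls as well as review of the electronic medical record".

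Sections 1.2 and 1.3 make SPADI change and adverse reactions primary endpoints and arthroplasty at 1 year a secondary one.

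**The concern.** The whole study treatment is given on the first day (section 7.2.2). Removing a patient afterwards withholds no study treatment. It only ends observation of a patient who has already received the randomised dose.

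Three kinds of planned data are lost:

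- **SPADI after removal.** A patient removed before 2 months has no change score for the t-test in section 8.3.
- **Adverse reactions after removal.** The reaction that led to removal is kept, but its later course and any further reactions are not collected.
- **Arthroplasty status at 12 months.**

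Patients removed for safety or non-adherence may differ from those who stay. Safety removals could also be related to dose, in a trial whose hypothesis (section 1.1) includes fewer side effects at the low dose. The loss may therefore be selective, and extra enrolment restores numbers without restoring comparability.

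**Working it through.** **Which rule governs.** Sections 7.2.3, 10.3 and 10.4 set general schedules and make no exception for withdrawn patients. Section 3.3.2 is the specific rule for them, so it prevails. This is not a contradiction between sections; the rule itself discards the data. Record review under 10.3 and the 12-month chart review need no reply from the patient, and they stop too.

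**Inputs from section 8.2.** Non-inferiority comparison: SD 20, margin 15, difference of 4 between adjacent doses, one-sided 2.5%, 80% power, 52 per group, 57 per group after a 10% allowance.

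**The plan's own figure.** n = 2 × [20 × (1.960 + 0.842) / (15 − 4)]² = 51.9, so 52 per group, as stated. 52/0.9 = 57.8, close to the stated 57. The allowance protects numbers: 57 × 0.9 = 51.3 patients give 79.5% power. It does nothing about which patients are lost.

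**Assumptions, not in the documents.** Removal before 2 months in 5% of one arm and 5%, 3% or 0% of the other (0.05 × 57 = 2.9 and 0.03 × 57 = 1.7 patients). The SPADI improvement of removed patients is 20 points less than that of retained patients, in both arms.

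**Bias.** If a share w is removed with deficit D, the mean of those retained exceeds the full-arm mean by w × D. The bias in a between-arm difference is b = (w_A − w_B) × D:

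- (0.05 − 0.05) × 20 = 0
- (0.05 − 0.03) × 20 = 0.4
- (0.05 − 0) × 20 = 1.0 point

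**Effect on the non-inferiority tests.** SE = 20 × √(2/52) = 3.92, with 52 analysed per arm throughout.

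| Quantity | Formula | b = 0 | b = 0.4 | b = 1.0 |
|---|---|---|---|---|
| One-sided error, lower-dose arm flattered | Φ(b/3.92 − 1.96) | 2.5% | 3.2% | 4.4% |
| Power, higher-dose arm flattered, lower dose 4 points worse | Φ((11 − b)/3.92 − 1.96) | 80.1% | 77.1% | 72.2% |
| Power, higher-dose arm flattered, lower dose 4 points better | Φ((19 − b)/3.92 − 1.96) | 99.8% | 99.7% | 99.6% |

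The error rate is taken at a true difference equal to the margin, so the margin cancels. The power rows need the 15-point margin. Section 8.3 gives .5 without a unit, so no power is computed for it. The last row is needed because the means listed in 8.2 (40, 36, 32 for low, medium, high) have the lower dose ahead, while the difference written beside them has the opposite sign.

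**Effect on the two-sided 20 mg versus 80 mg test.** With SD 40 and 51 per group from 8.2, SE = 40 × √(2/51) = 7.92. The same biases of 0.4 and 1.0 raise the 5% error to 5.03% and 5.18%. With SD 20 and 52 per group it becomes 5.1% and 5.7%.

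**Arthroplasty at 1 year.** Each patient of unknown status leaves the arm's rate undetermined by 1/57 = 1.8 percentage points; three patients leave 3/57 = 5.3 points.

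**The case against.** The strongest reply is that few patients are affected. Those who withdraw consent to data collection are lost under any wording. After one injection the protocol asks for little beyond answering remote contacts, so non-adherence will often mean not replying, and their SPADI would be missing anyway. That leaves mainly safety removals. Section 3.3.1 defines no specific post-injection trigger for these, and sections 2.1 and 16.4 describe serious side effects as rare. This stands as a limit on size. It does not cover safety removals who would still respond, or chart-based safety and arthroplasty data, which non-responders could also still provide.

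The numerical effects rest on assumed rates and on a deficit equal to a full SD, and they are small for the two-sided test. The power loss disappears under the means as listed. The 1.8 points per patient apply to unknown status from any cause. All of this is correct, and the figures should be read only as an illustration.

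Safety oversight partly remains. Section 10.5 says "Reporting of any adverse events will be reviewed as they occur", and section 19.1 requires reporting to the IRB of harm judged unexpected and probably related. Neither supplies the missing endpoint data.

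Finally, missing-data handling is the larger problem, since section 8.3 names no method even for the planned 10% loss. That is true, but data that could have been collected are better than any method for replacing them.

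**Conclusion.** The concern holds. Section 3.3.2 discards planned primary and secondary endpoint data for patients who have not withdrawn consent, and nothing elsewhere in the document restores them. This is a stated rule, not a missing detail.

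The size and direction of any bias cannot be established, because the documents give no removal rates. Bias is zero if removals and deficits are equal across arms. On the assumed imbalances it is 0.4 to 1.0 point on SPADI: modest, but enough to raise a one-sided 2.5% error to about 3.2% to 4.4% in the unfavourable direction. The power figures are conditional on the 15-point margin and on the lower dose being 4 points worse.

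The rule should be changed because the remedy is cheap and uncollected SPADI scores cannot be recovered later. Confidence is medium, since the number of patients affected is unknown and may be small.

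**What to change.** Replace the first sentence of section 3.3.2 with wording such as:

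> Data collection stops only when the patient withdraws consent to data collection. Patients removed for other reasons under 3.3.1 continue the planned 2-week, 2-, 4- and 6-month contacts and the 12-month contact and chart review (7.2.3), and are analysed in their assigned arm. The date and reason for removal are recorded.

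This concerns data collection only and leaves patient care unchanged.

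The cost is protocol wording and a few extra contacts, some of which will go unanswered. The contacts and the chart review are already planned. The consent and authorisation wording may need to match; those pages are not in the review copy, so this was not checked.

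The change does not settle how a patient with no follow-up SPADI enters the t-test in section 8.3. That needs its own rule. It should be made before removals occur.

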1.2 Primary Study Endpoints

- Change in Overall SPADI scores at baseline compared to 2,4, and 6 months.
- Adverse reactions to the steroid

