8.2 Sample size determination

This is a three arm trial comparing three different doses of steroid (20mg, 40mg, 80mg) in patients with glenohumeral arthritis. The primary endpoint is change in overall pain score on the SPADI at two, four, and six months from baseline. The sample size is determined based on assuming a minimal clinically meaningful difference in the 20mg vs 80mg groups as well as conducting non-inferiority tests in the 20mg vs 40mg and 40mg vs 80mg groups. Let d_1 , d_2 , and d_3 be the average change in overall pain scale for the three different doses (low, medium, high). For the first part, in the 20mg vs 80mg groups, we wish to have sufficient statistical power based on the assumption of a moderate Cohen effect size of .5 (e.g. differences of 40 vs 20 with a standard deviation of 40). This requires a sample size 51 per group based on a two-sided 80%-power 5%-level t-test. For the non-inferiority test, we assume d_1 , d_2 , and d_3 are 40, 36, and 32 (so $d_3-d_2=d_2-d_1=4$) with a standard deviation of 20. Allowing for a non-inferiority margin of 15 (so that differences less than 15 are deemed clinically non-inferior), a sample size of 52 per group based on an 80%-power 2.5%-level (since there are two tests) non-inferiority test (<http://powerandsamplesize.com/Calculators/Compare-2-Means/2-Sample-Non-Inferiority-or-Superiority>). Allowing for 10% loss to follow-up yields a final sample size calculation of **57 per group for each of the three groups**.

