8.3 Statistical methods

The primary endpoint is change from baseline of the shoulder pain and disability index (SPADI). The low dose and high dose changes will be analyzed with a two-sided two-sample t-test. Noninferiority tests with a margin of .5 will be used to test for a clinically meaningful difference between 20mg and 40mg doses and the 40mg and 80mg doses. The three groups will be summarized with descriptive statistics and univariate statistical tests using analysis of variance for normally distributed continuous variables, Kruskal-Wallis test for non-normally distributed continuous variables, and the Fisher's exact test for categorical variables. The demographic data and SPADI data will be analyzed accordingly. All statistical analyses, graphics, and reports will be prepared following best practices in conducting reproducible research in statistics utilizing various software packages built around the R software platform. [name]., Associate Professor, will serve as the Biostatistician for this study.

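### Section 8.3 names no missing-data method, so SPADI scores kept from patients who leave early go unused at later visits, which can bias the non-inferiority comparisons

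*Combined protocol and SAP*

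**What the plan says.** The primary efficacy endpoint is measured at three follow-up visits. Section 1.2 gives it as "Change in Overall SPADI scores at baseline compared to 2,4, and 6 months".

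On withdrawal, section 3.3.2 says "If a patient is withdrawn from the study, data collection will be terminated from that time point forward", and then "All prior data collected will be included in the analysis". Withdrawn patients are not to be "replaced, but instead more subjects may need to be enrolled". Sections 8.1 and 8.2 allow for 10% loss to follow-up.

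The efficacy methods are all in section 8.3. For the extreme doses: "The low dose and high dose changes will be analyzed with a two-sided two-sample t-test". For adjacent doses: "Noninferiority tests with a margin of .5 will be used to test for a clinically meaningful difference between 20mg and 40mg doses", and likewise for 40 mg and 80 mg. Three-group summaries use analysis of variance, Kruskal-Wallis or Fisher's exact test. Section 8.3 does not name a repeated-measures model, an imputation method, an analysis population, a missing-data sensitivity analysis, or the visit at which the tests are made.

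**The concern.** Every efficacy method in 8.3 compares groups on a change score. Without imputation, a patient can enter the comparison at a visit only with a SPADI at baseline and at that visit. For a patient who gives a 2-month score and then withdraws or stops replying, that score says something about the likely 4- and 6-month result, yet it plays no part in those comparisons.

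This matters most for non-inferiority. Suppose the lower dose works less well and patients with a poor early result are more likely to be lost. Then more are lost from the lower-dose arm, those who remain look better, and the observed deficit shrinks. Section 1.1 hypothesises that the low dose does as well as the higher ones, so an unspecified method that can favour that answer should be settled before analysis.

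**Working it through.** **1. What each patient contributes under 8.3 with no imputation**

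- Leaves before 2 months: no change score, so in no comparison of change.
- Leaves between 2 and 4 months: in the 2-month comparison only.
- Leaves between 4 and 6 months: in the 2- and 4-month comparisons only.

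**2. The plan's own allowance for loss**

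Inputs from 8.2: margin 15, SD 20, adjacent difference 4 (taken as the lower dose being worse), 2.5% level, 80% power.

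- n = 2 × [20 × (1.960 + 0.842) / (15 − 4)]² = 51.9, so 52 per group, as stated.
- For 10% loss: 52 × 1.1 = 57.2, or 52 / 0.9 = 57.8. The stated 57 fits the first and is one short of the second rounded up.
- After 10% loss, 57 × 0.9 = 51.3 remain, and power is Φ(11 / (20 × √(2/51.3)) − 1.96) = 79.5%.

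The allowance therefore protects precision when loss is unrelated to outcome. It does nothing about bias.

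**3. Illustration at the margin**

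From the documents: SD 20, margin 15, 57 randomised per arm, 10% loss, one-sided 2.5% test. Assumptions that are not in the documents:

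- Changes at 2 and 6 months are bivariate normal with correlation ρ of 0.4, 0.6 or 0.8.
- The deficit is the same at both visits.
- Each patient below a common 2-month cut-off c is lost with probability 0.5, with c set to give 10% loss overall.

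With a = (c − mean)/20, completers exceed their arm's true 2-month mean by 0.5 × 20 × φ(a) / (1 − 0.5 × Φ(a)). At 6 months the excess is ρ times that. For means 40 and 25 (deficit 15), c = 14.46.

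- Higher dose: a = −1.277; loss 0.5 × 0.101 = 5%; excess 10 × 0.1765 / 0.950 = 1.86.
- Lower dose: a = −0.527; loss 0.5 × 0.299 = 15%; excess 10 × 0.3472 / 0.850 = 4.08.
- Observed 6-month difference = 15 − ρ × (4.08 − 1.86) = 15 − 2.22ρ, which is 14.1, 13.7 and 13.2.

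The unequal loss was not imposed. One rule applied to both arms produces it. Simulated trials with these inputs wrongly declare non-inferiority in about 4%, 5% and 7% of cases. Regressing on the 2-month score brings the difference back to about 15.

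**4. The same rule at the planned difference of 4**

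For means 40 and 36, c = 21.08, and the excesses are 2.79 and 3.41. The bias is 0.62ρ, or about 0.2 to 0.5 points, so a true 4 appears as about 3.75 to 3.5.

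**5. Other assumed patterns**

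- Loss unrelated to response: no bias.
- Worst 10% lost from each arm, true difference 4: still 4.0.
- Worst 15% of the higher dose and worst 5% of the lower lost: 4 + 20 × 0.2332/0.85 − 20 × 0.1031/0.95 = 7.3, away from non-inferiority.
- Means as printed in 8.2 (40, 36, 32 from low to high), 10% loss of the poorest responders on the tested change itself: a shift of 0.6 to 1.1 against the low dose.
- Loss driven by the tested visit's own change, deficit 15, 10% loss: observed 11.0 to 12.7, false non-inferiority 9% to 22%.

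**The case against.** A reader might infer that 8.3 contradicts 3.3.2. It does not. A 2-month score from a patient who later withdraws still enters the 2-month comparison, and 3.3.2 does not promise that an early score will inform a later visit. Nor does the plan state that anyone is dropped. That follows from comparing change scores without imputation. The t-test is named only for 20 vs 80 mg, and the statistic for the non-inferiority tests is not given.

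A reader might also take bias towards non-inferiority as certain. The documents do not support that. Nothing in them says that poor responders leave more often. Treatment is a single injection, follow-up is by email, phone or mail, and the withdrawal criteria in 3.3.1 do not mention lack of effect. Other patterns give no shift or the opposite one.

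Two further cautions stand. The 4% to 7% is for a true deficit equal to a margin of 15, while 8.3 prints .5. If .5 means half an SD (an assumption; 0.5 × 20 = 10 points), the error at that boundary is 3.6% to 4.9%. The recovery to about 15 is also built in, because the assumed loss depends only on a recorded score. It does not show that a model would work if patients leave after worsening unseen.

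What remains is that the planned methods cannot use earlier scores at later visits, and that the trial already collects the data for a method that can.

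**Conclusion.** The point holds as a weakness in the choice of analysis. Section 8.3 is in effect complete-case at each visit, and the scores kept under 3.3.2 are only partly used. Under the assumed loss rule, the effect on the type I error of a non-inferiority test is modest but real: about 4% to 7% instead of 2.5% when the true deficit sits at 15. At the planned difference of 4 the bias is about half a point or less. The size rests on the assumed dropout rule and correlations. The direction rests on the lower dose being truly worse and on loss following poor early response. The change is worth making because it is cheap and the non-inferiority tests are central to the trial, not because bias is shown to be present.

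**What to change.** In 8.3, make the main analysis a repeated-measures mixed model of SPADI at 2, 4 and 6 months in all randomised patients, with arm, visit, arm-by-visit and baseline SPADI. With baseline as a covariate, a patient with no follow-up score still drops out of the model. To include these patients, enter baseline as an outcome, with arm means constrained equal at baseline.

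- Take the 20 vs 80, 20 vs 40 and 40 vs 80 mg contrasts and confidence intervals from the model at a named visit.
- Keep the two-sample t-tests as a sensitivity analysis.
- Add a sensitivity analysis for data not missing at random, for example by worsening the assumed later scores of lost patients by increasing amounts, differently by arm.

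The cost is SAP wording only, with no new patients, visits or data. The downside is that the model assumes that loss depends on recorded scores, which is why the last item is needed. Separately, the margin must be reconciled before any non-inferiority test is run: 8.2 has "Allowing for a non-inferiority margin of 15" and 8.3 has .5.
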